5.1 Inclusion Criteria

Participants are eligible to be included in the study only if all of the following criteria apply:

Age

1. Participant must be 18 to 60 years of age inclusive, at the time of signing the informed consent.

Type of Participant and Disease Characteristics

2. Participants with a primary diagnosis of acute sports-related acute soft tissue injuries of the lower extremities that do not require hospitalization and that occurred within 3 hours of enrollment.
3. Participants with a baseline algometric measurement values on the injured site of $\leq 50\%$ of the respective value at the contralateral site.
4. Participants with a baseline (POM) of ≥ 50 mm on a visual analog scale (VAS) (0–100 mm).
5. Participant's absolute sensitivity to tenderness on the contralateral site is at least 2.5 N/cm² as measured by algometry.
6. Participant's size of trauma is between 25 and 150 cm².

Informed Consent

7. Capable of giving signed informed consent as described in Section 10.1.4 which includes compliance with the requirements and restrictions listed in the informed consent form (ICF) and in this protocol.

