8.1.2 Baseline Visit 1 - (Day 1)

Patients will undergo baseline pain and tenderness testing to determine eligibility for randomization. All patients must score at least 50 on the 0 – 100 mm visual analog scale (VAS) for POM and have algometric measurement values on the injured site of $\leq 50\%$ of the respective value at the contralateral site in order to qualify for treatment. Additionally, the absolute tenderness sensitivity of the contralateral site must be at least 2.5 N/cm^2 . The investigator will stratify patients into 2 injury cohorts. One cohort is contusion cohort and the other is the sprain/strain cohort. The contusion cohort will enroll at least 50 patients and the sprain/strain cohort will enroll at least 25 patients.

The site will randomize Investigational Medicinal Product (IMP or treatment kit) based on computer generated randomization schedule stratified by injury type (either contusion or sprain/strain cohorts).

Patients entering the Treatment Phase are randomized in a 2:2:1 fashion into one of three blinded treatments:

- Naproxen Topical Gel, 10%, every 12 hours for 5 days
- Diclofenac Diethylamine Topical Gel, 2.32% every 12 hours for 5 days
- Placebo Topical Gel every 12 hours for 5 days

Patients will be reminded to discontinue use of all pain medications including supplements, use of topical heat or cold, and other products of topical application once the patient is deemed eligible to participate.

The investigator or designee will mark the injured lower extremity with a water-resistant pen so that the treatment area is consistently targeted through the Treatment Phase. After randomization, the ***first*** topical treatment will be applied the evening of Day 1. The topical treatment will be weighed on a digital scale, then applied by an unblinded study staff at the site who is not responsible for adverse events, global assessments, pain and tenderness measurements. Patients will wear a blindfold during treatment so that the identity of the IMP is blinded. Patients will be instructed to return approximately 12 hours to the site for their ***second*** treatment. The nominal repeat dosing times will be established for the rest of the study that conform to the dosing time established on Day 1.

Rescue medication will be dispensed. If the patient decides to take rescue medication prior to the next treatment, the patient will be instructed to complete the Global Assessments prior to taking the rescue medication.

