9.4.2 Primary Endpoint

The primary efficacy variable is:

- Tenderness (Algometry) over the initial 72 hours (Algometry AUC 0-72).

The primary efficacy endpoint will be analyzed if deemed necessary using analysis of covariance (ANCOVA) with treatment as the factor and baseline tenderness (algometry) as the covariance. Pair-wise comparisons may be made from above model.

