6 SAMPLE SIZE

This is a proof-of-concept study and therefore a specific statistical power calculation cannot be applied, however, assuming a comparable effect of the test gel vs. diclofenac – as suggested by pharmacological studies, reference is made to similar studies (Predel, Br J Sports Med 2004;38:318–323), in which the standardized effect sizes of Algometry AUC 0-72 and POM VAS AUC 0-72 were over 1; with 30:15 patients, a drop-out rate of 10 %, and a two-sided significance level $\alpha = 5\%$, a power $1 - \beta$ of about 80 % is reached.

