14.4 Efficacy

14.4.1 Primary efficacy variable

The primary efficacy variable is:

- Tenderness (Algometry) over the initial 72 hours (Algometry AUC₀₋₇₂).

For the comparison of the test gel vs. placebo, the primary efficacy hypothesis to be tested is the equality of Algometry AUC₀₋₇₂, i. e.

$$H_0: \mu_T = \mu_P \text{ vs. } H_1: \mu_T \neq \mu_P.$$

The primary efficacy endpoint will be analyzed using analysis-of-covariance (ANCOVA) with treatment as the factor and baseline tenderness (algometry) as the covariate. Pair-wise comparisons may be made from above model.

The primary analysis population is the Per protocol population (PP).

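### The primary ANCOVA omits the baseline contralateral algometry reading that every randomised patient has, a cheap covariate that may narrow the confidence interval

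*SAP*

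**What the plan says.** Protocol 5.1 admits a patient only if the injured-site algometry value is at most 50% of the value at the contralateral site. A further criterion sets a floor of 2.5 N/cm² for "Participant's absolute sensitivity to tenderness on the contralateral site". Protocol 8.1.2 repeats this as a condition for randomisation: "the absolute tenderness sensitivity of the contralateral site must be at least" that figure. Both readings therefore exist at baseline for every eligible randomised patient.

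The primary variable is Algometry AUC 0-72. SAP 14.4.1 gives the model: "The primary efficacy endpoint will be analyzed using analysis-of-covariance (ANCOVA) with treatment as the factor and baseline tenderness (algometry) as the covariate". Protocol 9.4.2 has the same model, "with treatment as the factor and baseline tenderness (algometry) as the covariance". Neither section names the site. Protocol 4.1.1.1 describes tenderness as a measurement on the injured area. The separate injured/contralateral ratio endpoint in Protocol 9.4.4 and SAP 14.4.3 implies that the primary AUC is the unscaled injured-site value.

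The general model for quantitative outcomes in SAP 14.4.3 adds center but no contralateral term. The contralateral reading is analysed only in the ratio AUCs over 72 and 120 hours, among the other efficacy variables. No reason is given for leaving it out elsewhere.

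**The concern.** Higher algometry values mean less tenderness (Protocol 4.1.1.2), so recovery is a rise in the pressure threshold. The injured-site baseline says where a patient starts. The contralateral value is the best available estimate of where that patient would end up once healed.

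Take two eligible patients who both start at 2 N/cm², one with a contralateral value of 4 and one with 10. If each closes half of the gap linearly by 72 hours, they end at 3 and 6. Their AUCs are 72 × (2 + 3)/2 = 180 and 72 × (2 + 6)/2 = 288 N/cm²·h. The planned model treats them as having the same expected AUC on the same treatment.

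At stake is the width of the naproxen–placebo interval in a small trial meant to guide a development decision (Protocol 2.1).

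**Working it through.** **1. The plan's own power figure.** SAP 6 takes standardized effects for which "the standardized effect sizes of Algometry AUC 0-72 and POM VAS AUC 0-72 were over 1", and 45 patients: "with 30:15 patients, a drop-out rate of 10" per cent. It concludes that power "of about 80 % is reached" at two-sided 5%.

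- Patients after drop-out: 30 × 0.9 = 27 and 15 × 0.9 = 13.5.
- At effect size 1.0: 1/√(1/27 + 1/13.5) = 1/0.333 = 3.00, and Φ(3.00 − 1.96) = 85.1%. The exact t calculation gives 83.3%.

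The stated 80% is therefore slightly conservative, and it is met without the contralateral covariate.

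**2. What a second covariate can do.** Let r be the partial correlation of the contralateral baseline with AUC 0-72, given the injured-site baseline. The standard error is multiplied by √(1 − r²). The documents give no value for r. The power column takes effect size 1.0 as already baseline-adjusted: Φ(3.00/√(1 − r²) − 1.96).

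| r (assumed) | Fall in standard error | Power |
|---|---|---|
| 0 | 0% | 85.1% |
| 0.2 | 2% | 86.5% |
| 0.3 | 5% | 88.2% |
| 0.4 | 8% | 90.5% |
| 0.5 | 13% | 93.4% |
| 0.6 | 20% | 96.3% |

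At an assumed effect of 0.8, power is about 67%. It rises to about 71% at r = 0.3 and 79% at r = 0.5.

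**3. Which gains are plausible.** This was simulated with a trapezoidal AUC over 12-hourly readings. Every gain is measured after adjustment for the injured-site baseline, and every input is an assumption.

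If the injured site recovers towards the contralateral value:

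- *Exponential recovery, 18 scenarios.* Normal threshold mean 8 N/cm² with CV 20–40%, injured baseline 20–50% of normal, median time constant 48–192 h, reading error SD 0.5–1.0 N/cm², entry criteria applied. Residual variance is multiplied by 0.81 to 0.47, so the standard error falls by 1 − √0.81 = 10% to 1 − √0.47 = 31%.
- *Linear recovery, 27 scenarios.* CV 20–40%, injured share from 10%, 30% or 45% up to 50%, on average 30–90% of the deficit closed by 72 h, 10% measurement error. The injured baseline alone explains 50–90% of AUC variance. Partial r is 0.31 to 0.81 with median 0.50, so the standard error falls by 5% to 41%, median 13%. Only two scenarios exceed 30% (r = 0.76 and 0.81).
- *Exponential recovery with a wider spread of healing rates* (log-SD 1.0 rather than 0.5): 6–18%.
- *Exponential recovery with reading error SD 2.0 N/cm²*: 3–21%. This case matters because Protocol 8.2.2 raises pressure at 10 N/cm² per second, so an SD of 0.5–1.0 is only 0.05–0.1 s of reaction time.

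If recovery does not depend on the contralateral value:

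- *Recovery proportional to the injured baseline*: 1–9%.
- *Recovery by an unrelated absolute amount*: 0.4–7%.

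A further run gave 3–38% when recovery is towards the contralateral value and 0–11% when it is not.

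**4. The cost if it is uninformative.** The lost degree of freedom alone moves t-based power at 27:13 from 82.3% to 82.2%. In all, an uninformative covariate costs about 1–3% on the standard error at 40–67 patients. Setting (1 + cost) × √(1 − r²) = 1, it pays for itself once r exceeds about 0.14 (cost 1%) to 0.24 (cost 3%).

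**The case against.** The planned model is standard and defensible: the baseline of the outcome is the usual ANCOVA covariate, and no passage conflicts with it. Four arguments support leaving it alone.

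- **The injured baseline already carries much of the information.** This stands. It is at most half of the same person's contralateral value and explained 50–90% of AUC variance in the linear-recovery scenarios. A reader might infer that the analysis leaves all normal between-person differences as noise. The documents do not support that; only the remainder is at issue.
- **The gain depends on the healing model.** This also stands. No passage says that the injured site recovers towards the contralateral value within 72 hours. An r of 0.2 or less, worth under 2 points of power, cannot be excluded.
- **Nothing is invalid.** Correct. A reader might infer bias from a chance imbalance in the 15-patient placebo arm. At 27:13.5 that imbalance has an SD of √(1/27 + 1/13.5) = 0.33 patient-SDs, but it is ordinary sampling variation that the standard error already reflects. Nor is the trial shown to be underpowered, as step 1 shows.
- **The ratio AUC 0-72 already compares each patient with the uninjured side.** Partly so. It will be reported with a 95% interval, and rank among endpoints matters less in a proof-of-concept trial without multiplicity adjustment. It does not sharpen the estimate for the primary variable.

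**Conclusion.** The point holds as one of efficiency. A baseline value that is plausibly prognostic, and is available for every randomised patient, is left out of the primary model without a stated reason.

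The reduction in standard error cannot be derived from the documents. Under assumed healing models it is near 0 to about 10% if recovery does not depend on the contralateral level. It is about 3% to somewhat over 30% if recovery is towards that level, with about 40% in the single most favourable scenario. The case for the change rests on the asymmetry between these ranges and a cost of about 1–3%. It does not rest on any one simulated figure.

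The conclusion also assumes that the primary AUC and its baseline covariate are injured-site values, which the documents imply but SAP 14.4.1 does not say.

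**What to change.** Before unblinding, make these changes in SAP 14.4.1 and Protocol 9.4.2:

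- Add baseline contralateral-site algometry as a second continuous covariate in the primary ANCOVA.
- Use the same covariate in the other injured-site algometry AUC and change-from-baseline analyses.
- State that the primary AUC and the baseline tenderness covariate refer to the injured site.

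SAP 1 has the SAP finalised after the blind review meeting, and SAP 12 places that meeting before unblinding, so the plan's own timetable leaves room. No new data are needed. The cost is a few sentences of text and the one degree of freedom already counted.

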6.4 Measures to Minimize Bias: Randomization and Blinding

| | |
|---|---|
| Study using Pre-Coded Randomization provided to the site | On Day 1 participants will be assigned a unique number (randomization number) in ascending numerical order at each study site. The randomization number encodes the participant's assignment to one of the 3 arms of the study, according to the randomization schedule generated prior to the study by the Statistics Department at Bayer. Each participant will be dispensed blinded study intervention, labeled with his/her unique randomization number, throughout the study. |
| Blind Break (Envelopes) | A sealed envelope that contains the study intervention assignment for each participant will be provided to the investigator. The sealed envelope will be retained by the investigator (or representative) in a secured area. In case of an emergency, the investigator has the sole responsibility for determining if unblinding of a participant's intervention assignment is warranted. Participant safety must always be the first consideration in making such a determination. If the investigator decides that unblinding is warranted, the investigator should make every effort to contact the sponsor prior to unblinding a participant's intervention assignment unless this could delay emergency treatment of the participant. If a participant's intervention assignment is unblinded, the sponsor must be notified within 24 hours after breaking the blind. Once the study is complete, all envelopes (sealed and opened) must be inventoried and returned to the sponsor. |

| | |
|---|--|

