For quantitative outcomes assessed each null hypothesis will be tested with an analysis-on-covariance (ANCOVA) model including treatment group and center as main effects, and the baseline value as covariate (those outcomes for which there is a baseline). The model will be fit both with and without the treatment-by-center interaction. The primary model will be the model without the interaction. If the treatment/center interaction is statistically significant ($p < 0.05$), additional ANCOVAs will be run to identify the center(s) driving the interaction and to lay out the evidence for efficacy among the centers whose results are concordant and centers driving the interaction. ANCOVA outputs will be presented in the Statistical Appendix for the primary and various secondary outcomes to allow an outside reviewer to assess the acceptability of the primary statistical model.

The treatment effects will be estimated as mean differences between the active and placebo groups and between the two active groups with 95% confidence intervals.

The percentage of subjects with no VAS POM at 120 hours will be analyzed by means of Fisher's exact test.

The ordinal outcome (global assessment of treatment efficacy)) will be analyzed by the Cochran-Mantel-Haenszel test of general association, stratified by center and also by subgroup (strain/sprain, contusion).

Statistical test results for secondary variables will only be interpreted exploratorily.

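### The SAP carries two ANCOVAs that can each be read as the primary analysis of Algometry AUC 0-72, one without centre and one with it, and no sentence says which decides the naproxen-placebo test

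*SAP*

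**What the plan says.** SAP 14.4.1 states the primary hypothesis as equality of the test-gel and placebo means for Algometry AUC 0-72. The analysis is "analysis-of-covariance (ANCOVA) with treatment as the factor and baseline tenderness (algometry) as the covariate. Pair-wise comparisons may be made from above model". Protocol 9.4.2 gives the same two-term model.

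SAP 14.4.3, headed for the other efficacy variables, reads: "For quantitative outcomes assessed each null hypothesis will be tested with an analysis-on-covariance (ANCOVA) model including treatment group and center as main effects", with the baseline value as covariate where one exists. The model is fitted with and without treatment-by-centre interaction, and "The primary model will be the model without the interaction". ANCOVA outputs will be shown "for the primary and various secondary outcomes to allow an outside reviewer to assess the acceptability of the primary statistical model". The same section commits to estimating active-placebo differences with 95% confidence intervals.

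SAP 14.6 also plans an ANCOVA with treatment-by-site interaction for the primary variable.

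On design, protocol 4.1 gives three sites and names injury type as the stratification factor. Protocol 6.4 issues randomization numbers "in ascending numerical order at each study site".

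**The concern.** The primary hypothesis should have one pre-specified p-value. Here two models have a claim to it: one by section heading and protocol, the other by its own label and its stated reach to the primary outcome. SAP section 1 says the plan is finalized only after the data blind review meeting, so the choice should be fixed in the text and not left to whoever programs the tables.

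The choice can matter. About 27 naproxen and 13 placebo patients are expected in the comparison, and the trial is meant to guide a development decision (protocol 2.1). If sites differ in level, for example through different algometer operators, a model without centre leaves that difference in the residual. The wording that pairwise comparisons *may* be made adds to the looseness, because the stated hypothesis is itself a pairwise comparison.

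**Working it through.** **1. The two models side by side**

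| | SAP 14.4.1 / protocol 9.4.2 | SAP 14.4.3 |
|---|---|---|
| Terms | treatment, baseline | treatment, centre, baseline |
| Claim to be primary | heading of 14.4.1; protocol | labelled the primary model; outputs promised for the primary outcome |
| Naproxen-placebo contrast | optional (*may*) | difference with 95% CI will be estimated |
| Injury type | absent | absent |

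**2. The plan's own power figure.** SAP section 6 gives 30:15 patients, 10% drop-out, two-sided 5%, standardized effect over 1, and power of about 80%. Analysed: 30 × 0.9 = 27 and 15 × 0.9 = 13.5, taken as 13. At an effect of exactly 1.0:
- SE = √(1/27 + 1/13) = 0.338 SD, so the noncentrality is 1/0.338 = 2.96.
- A two-sample t-test gives 82.3% (83.3% at 27:13.5).
- A rank test with relative efficiency 0.955 gives 80.4%.

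The plan's figure is therefore reproduced approximately.

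**3. Power and interval width under each model.** The arms are 27/27/13, 67 in all. Residual df are 67 − 4 = 63 without centre and 67 − 6 = 61 with it. Let ρ be the share of AUC variance lying between sites. The documents give no value, so ρ is assumed, with total variance held fixed and baseline not carrying the site difference.
- Without centre: noncentrality 2.96; CI half-width 1.998 × 0.338 = 0.675.
- With centre: noncentrality 2.96/√(1 − ρ); half-width 2.000 × 0.338 × √(1 − ρ). At ρ = 0.10 this is 0.640, and 0.675/0.640 is about 1.05.

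| ρ | Power without centre | Power with centre | No-centre CI wider by |
|---|---|---|---|
| 0 | 83.1% | 83.0% | −0.1% |
| 0.05 | 83.1% | 84.9% | 2.5% |
| 0.10 | 83.1% | 86.7% | 5.3% |
| 0.20 | 83.1% | 90.3% | 11.7% |
| 0.30 | 83.1% | 93.6% | 19.4% |

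**4. Is the no-centre standard error right?** Simulation: 75 randomized 2:2:1, three equal sites, 10% lost, 5,000 trials per setting, no treatment effect.

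| Allocation | ρ | No-centre: mean SE / true SD | Type I error without / with centre |
|---|---|---|---|
| Blocks of 5 within site | 0.1 | 0.336 / 0.317 | 3.9% / 4.8% |
| | 0.2 | 0.337 / 0.306 | 3.2% / 5.0% |
| | 0.3 | 0.337 / 0.286 | 1.9% / 4.9% |
| No balance by site | 0.1 | 0.336 / 0.337 | 5.2% / 5.0% |
| | 0.2 | 0.336 / 0.335 | 4.8% / 4.7% |
| | 0.3 | 0.336 / 0.343 | 5.4% / 5.1% |

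With balance by site, the no-centre SE is too large and the test conservative. Without it, the SE is correct but larger than the centre model's (0.323, 0.305 and 0.286).

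At ρ = 0 and effect 1.0, adding centre changed power from 84.3% to 84.0% with balance by site and from 83.3% to 82.5% without.

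**5. If baseline carries the same site shift.** Simulation: sites of 30/25/20, blocks of 5 within site, 10% lost, within-site baseline R² 0.2, effect 0.86, 4,000 trials.

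| ρ | No site shift in baseline: power without / with centre | Same shift in baseline: power without / with centre |
|---|---|---|
| 0.1 | 81% / 84% | 82.9% / 83.8% |
| 0.2 | 80% / 88% | 87.3% / 88.2% |

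With the shift in baseline, the gain from centre is 0.9 points in both rows. Over all the settings tried it lay between 0 and 1.5 points.

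**6. Disagreement.** The two models fell on opposite sides of p = 0.05 in about 1% to 12% of simulated trials. The low end comes from sites that do not differ. The high end comes from a 20% site share with allocation not balanced by site.

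**The case against.** The best defence is that the specific section governs: 14.4.1 and protocol 9.4.2 agree, and the centre model stands under a heading for other variables. That is a fair reading, and it may be what the author meant. It does not settle the matter, because the 14.4.3 paragraph itself reaches the primary outcome and calls its own model primary.

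The size of the loss is also open to challenge, and that challenge largely stands. Site variance is assumed throughout. An operator effect would probably appear in baseline algometry too, which is already a covariate. Protocol 8.2.2 standardizes the measurement (calibrated device, constant pressure increase, covered display). The trial is a proof of concept without multiplicity control, and nothing here raises the false-positive rate.

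A reader might infer two stronger things that the documents do not support:

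- **That the no-centre intervals are too wide whenever sites differ.** This needs allocation balanced within site. Numbers ascending at each site suggest separate lists, but no block size or blocking by site is stated, and the declared stratification factor is injury type.
- **That the overall treatment test might serve as the primary test**, so that an effect of diclofenac alone could count as success. SAP 14.4.1 and protocol 9.1 both state the hypothesis as test gel against placebo, and no passage gives the overall test that role. Only the loose *may* needs correcting.

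**Conclusion.** The point holds as an unresolved overlap with a modest, conditional cost. Two models can be read as the primary analysis, and the text does not choose between them.

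The no-centre model is never materially better. It is less precise if sites differ in ways that baseline algometry does not capture: about 3 to 8 points of power at an assumed 10% to 20% site share, shrinking to between 0 and 1.5 points if baseline carries the same shift. Its standard error is strictly too large only under within-site balance, which is suggested but not stated. Otherwise it is valid and merely less efficient. The sizes are scenarios, since the documents give no between-site variance; the conflict in the text does not depend on them.

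**What to change.** Before unblinding, revise SAP 14.4.1 to:

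1. Name one primary model: treatment, centre and baseline algometry, without interaction. This is already the 14.4.3 model.
2. Decide in the same edit whether injury type, the declared stratification factor, also enters. Neither current model contains it.
3. Define the primary p-value as the two-sided 5% naproxen-minus-placebo LS-mean contrast from that model, and replace *may* with *will*.
4. Keep the treatment-plus-baseline model as a labelled sensitivity analysis, and word 14.4.3 so that it no longer competes with 14.4.1.
5. Record the change from protocol 9.4.2 and the reason for it.

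The cost is one paragraph, a documented departure from the protocol text, and two residual degrees of freedom for centre: up to about 1 point of power if the sites do not differ.
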